6. STUDY DESIGN

Single centre prospective observational cohort study.

7. STUDY SETTING/LOCATION

Single centre study conducted at St John of God Midland Public and Private Hospitals (SJGMPPH).

8. STUDY POPULATION

The study population is consecutive patients admitted to St John of God Midland Private and Public hospital with a primary diagnosis of severe acute exacerbation of COPD (AECOPD). An AECOPD is defined as acute worsening of respiratory symptoms that results in additional therapy: antibiotics and/or systemic corticosteroids. Admission to hospital usually implies severe exacerbation of COPD. As this is an exploratory study a total of **80** patients will be recruited.

9. ELIGIBILITY CRITERIA

9a. Inclusion criteria

- Age ≥ 40 years
- Smoking history ≥ 15 pack years
- Suspected or Known COPD defined as a FEV1/FVC ratio of <70% on spirometry
- Hospital admission with primary diagnosis of AECOPD

9b. Exclusion criteria

- Patients who do not have airflow obstruction on spirometry (FEV1/FVC<70%)
- Patients in acute respiratory failure requiring non-invasive positive pressure ventilation or invasive mechanical ventilation
- Patients requiring ionotropic support
- Patients with concurrent diagnosis of bronchiectasis, interstitial lung disease, pulmonary embolism or acute cardiac failure
- Overseas and Interstate visitors

10. STUDY OUTCOMES

10a. Primary Outcome

 Hospital re-admission for COPD within 12 months defined as admitted to hospital, excluding emergency department presentation only, with discharge diagnosis on the discharge summary being "Exacerbation of COPD".

10b. Secondary Outcome(s)

- Time to hospital re-admission for COPD (up to 12 months)
- Repeat exacerbation of COPD within 12 months, defined as an acute worsening of respiratory symptoms that results in increased dose of systemic corticosteroids and /or antibiotics. This outcome will be self reported.
- Change in FeNO levels between Day 1 of admission and on follow-up visit at 6 weeks.
- Change in FEV1, FVC, FEV1/FVC between Day 1 of admission and on follow-up visit at 6 weeks.
- Change in CAT score between Day 1 of admission and on follow-up visit at 6 weeks.

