11. STUDY PROCEDURES

11a. Recruitment of participants

Screening will take place before consent. The respiratory physician involved in the study will approach potential study participants within 24 hours of admission for a primary diagnosis of AECOPD. If they fulfill inclusion criteria and have no exclusion criteria they will be invited to participate in this study. They will be provided with written information about the research and given the opportunity to ask questions regarding participation. The participant will have up to 2 hours to decide if they wish to participate. Once informed consent is given they will be considered participants. We aim to recruit 80 participants. From a small audit (10 patients) performed in 2017 we expect that 60% of patients asked to participate will be able perform FeNO and spirometry testing essential for recruitment. Those who cannot complete either FeNO or spirometry will be excluded from final analysis as they cannot contribute to the primary outcome. However, as this is a potential source of bias we will collect all other data and follow-up outcomes from these patients also. We expect 12 months will be necessary to recruit 80 patients who can perform both FeNO and Spirometry on admission.

11b. Randomisation

This is a prospective observational cohort study. No randomization is required. No case matching is required.

11c. Study procedure

We will approach potential study participants within 24 hours of admission for a primary diagnosis of AECOPD. If they fulfill inclusion criteria and have no exclusion criteria they will be asked to participate in this study. Once informed consent is given they will be considered participants. Patient questionnaire, FeNO and spirometry testing will be performed at Day 1 (recruitment day) and at 6-week follow-up appointment. A further questionnaire via phone contact will be performed at 3, 6, 9 & 12 months. If the participant cannot be contacted by phone, the study will contact the nominated next-of-kin and general practitioner. The patient's general practitioner will be informed of study participation. This study does not involve any treatment intervention. All additional tests, except FeNO measurement, are considered part of usual care. Additional tests include spirometry and blood testing (FBC, IgE and RAST) and will be used to identify individuals who may have Asthma COPD Overlap Syndrome (ACOS). These tests can be "added on" to bloods taken on admission. The study does not

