require additional follow-up appointments as the 6 week follow-up of these patients is part of usual care. An extra phone contact with the patients will be made at 3, 6, 9 & 12 months.

Day one:

- Location: SJOG hospital medical ward inpatient room
- Duration: 30 minutes
 - Informed Consent 10 minutes
 - Questionnaire 5 minutes
 - FeNO testing 5 minutes
 - Spirometry testing 10 minutes
- Baseline data collection form
 - Questionnaire
 - patient demographics, Charlson Comorbidity Index, COPD Assessment test, modified MRC dyspnea scale, Hospital Anxiety and Depression Scale
 - Laboratory blood tests
 - Full blood picture as per usual medical care. Retrieved from hospital pathology program.
 - IgE and RAST testing added This is usual clinical care to identify individuals who may have ACOS.
 - o Radiology CXR as per usual medical care. Retrieved from hospital radiology program
 - Treatment as per usual medical care documented from hospital patient medical file
- FeNO bedside measurement
- Spirometry testing

Early Post-Hospital Discharge:

• Researcher staff only – interrogating electronic medical records to determine discharge date and corticosteroid medication prescriptions during and after hospitalization.

6 week follow-up:

- Location: SJOG hospital medical outpatient clinic
- Duration: 30 minutes
 - o Questionnaire 5 minutes. (COPD Assessment test, modified MRC dyspnea scale)
 - FeNO testing 5 minutes
 - Spirometry testing 10 minutes
 - Blood testing 10 minutes
- 6 week data collection form
- Laboratory blood tests FBC, CRP, IgE
- FeNO bedside measurement
- Spirometry testing

3,6,9 & 12 month follow-up:

- Location: Phone contact only
- Duration: 5 minutes
 - Questionnaire 5 minutes
- 3, 6, 9 &12 month data collection form

• If the patient is unable to be contacted, consent will have been obtained to contact the nominated next of kin and General Practitioner to obtain any hospital admission discharge summary to determine the primary outcome.

11d. Measurement tools used

Fraction of Expired Nitric Oxide

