12. STATISTICAL CONSIDERATIONS AND DATA ANALYSIS

12a. Sample size and statistical power

This is an observational study without a pre-specified sample size. Based on pilot data and numbers of COPD admissions, we anticipate 80 participants will be both feasible and sufficient to examine the primary outcome.

12b. Statistical methods

Predictors for the primary outcome (readmission for COPD exacerbation) will be identified by using a multivariate logistic regression model incorporating FeNO level and other known and suspected factors associated with COPD readmissions. Associations between FeNO and readmission will be presented as odds ratios. Systemic steroids can affect FeNO measurements. Therefore, outcomes will also be analysed by dose of systemic corticosteroid prior to FeNO measurement.

Predictors of the secondary outcomes (time to readmission for repeat exacerbation of COPD and time to repeat exacerbation) will be identified by using a Cox Proportional Hazards regression model or logistic regression model as appropriate incorporating FeNO level and other known and suspected NORAD Protocol V1.2

March 2018

factors associated with COPD readmissions. Associations between FeNO and readmission will be presented as hazard ratios (Cox Proportional Hazards model) or odds ratios (logistic regression model).

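### The definition of repeat exacerbation lets escalation of index treatment count as a new event, and no collection of this outcome is specified before the 3-month call

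*Protocol*

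**What the plan says.** Protocol section 10b makes repeat exacerbation within 12 months a secondary outcome, "defined as an acute worsening of respiratory symptoms that results in increased dose of systemic corticosteroids and /or antibiotics. This outcome will be self reported". Section 8 defines the index event in other words: "An AECOPD is defined as acute worsening of respiratory symptoms that results in additional therapy: antibiotics and/or systemic corticosteroids".

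Section 12b names two time-to-event outcomes, "time to readmission for repeat exacerbation of COPD and time to repeat exacerbation", and assigns them to a "Cox Proportional Hazards regression model or logistic regression model as appropriate". Section 10b lists time to readmission but, for repeat exacerbation, only occurrence within 12 months.

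On collection, section 11c says: "A further questionnaire via phone contact will be performed at 3, 6, 9 & 12 months". At the 6-week visit the questionnaire entry reads "Questionnaire 5 minutes. (COPD Assessment test, modified MRC dyspnea scale". A 6-week data collection form is also listed, without its content. Soon after discharge, staff search the electronic record for the discharge date and for "corticosteroid medication prescriptions during and after hospitalization".

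For participants who cannot be reached, the main text of section 11c sends the study to the next of kin and general practitioner without limiting the purpose. The consent text in section 13 allows that contact for the 3, 6, 9 and 12 month calls and, as a separate purpose, for access to discharge summaries. The follow-up schedule within section 11c describes the contact only as a way to obtain "any hospital admission discharge summary to determine the primary outcome".

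**The concern.** A repeat event has to be told apart from the episode that brought the patient into the study. Every participant is approached within 24 hours of admission for an exacerbation, so observation begins while that episode is under treatment. The definition does not say when a repeat event may begin, and its wording about dose describes a step-up of ongoing treatment more naturally than it describes a new course.

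This matters for FeNO in particular. Day 1 FeNO is measured in the same episode, and section 5 hypothesises two things about it: higher FeNO goes with higher readmission risk, and higher FeNO goes with a better response to steroids. If both are true, an early escalation for poor response would tend to occur at low FeNO and a later new exacerbation at high FeNO. Counting both as one event would blur the FeNO association and leave the hazard ratio without a clear meaning.

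The timing of collection adds a second problem. A Cox model needs onset dates, and the protocol specifies no enquiry about this outcome in the weeks straight after discharge.

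**Working it through.** The protocol gives no event rate, power or target count for this outcome, and section 12a says there is no pre-specified sample size. There is no figure to reproduce, so the check is mainly a comparison of texts.

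**Step 1. Does escalation of index treatment meet the definition?**
- Section 10b requires (a) an acute worsening of respiratory symptoms and (b) a resulting higher dose of systemic corticosteroids and/or antibiotics.
- It does not require discharge, the end of the index course, or any recovery interval.
- Section 11a places enrolment within 24 hours of admission, and section 8 defines the index event by treatment with the same drug classes.
- A participant who worsens on the ward and has treatment stepped up therefore satisfies (a) and (b). The word repeat implies a new episode but gives no rule for recognising one.
- Conversely, a new course in someone on no treatment fits section 8 directly. It fits section 10b only if starting from nothing is read as a dose increase.

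**Step 2. When is the outcome first asked about?**
- Named at 6 weeks: CAT and mMRC. Neither records exacerbations. The content of the 6-week form is not given.
- Named soon after discharge: a record search that covers corticosteroids but not antibiotics, and that is not linked to this outcome.
- First phone questionnaire: 3 months, about 13 weeks. An event before the 6-week visit would first be asked about at least 13 − 6 = 7 weeks after that visit, and the longest recall is about 13 weeks. With an enquiry at 6 weeks, the longest recall in this first interval falls to about 7 weeks.

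**Step 3. How busy is that early window?** Section 2 gives background readmission of up to 15% at 30 days and up to 35% at 90 days. Applied to the planned 80 participants:
- Day 30: 80 × 0.15 = 12
- Day 90: 80 × 0.35 = 28
- Day 42, with a constant hazard between days 30 and 90: hazard = [ln(0.85) − ln(0.65)] / 60 = 0.00447 per day. Cumulative proportion = 1 − 0.85 × exp(−12 × 0.00447) = 0.194. Count = 80 × 0.194 = 15.6, about 16.

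These are upper-end rates, and section 2 does not say that all such readmissions are for COPD. They show that many first events may precede the 3-month call. They do not count recall-dated events, because a readmission can be dated from its discharge summary. The events that depend on recall are those treated in the community, for which the protocol gives no rate.

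**Step 4. What happens when a participant cannot be reached?** The main text of section 11c and purpose 1 in section 13 let next of kin or the practice stand in for the call. The follow-up schedule in section 11c limits that contact to discharge summaries for the primary outcome, and section 10b calls repeat exacerbation self-reported. The protocol does not say whether a proxy or practice report counts for this outcome.

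**The case against.** The other side has a fair case, and several stronger readings do not survive it.

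- A reader might infer that unreachable participants have no source at all for this outcome and would be scored event-free. The documents do not support that. Sections 11c and 13 provide for next-of-kin and general practitioner contact in place of the call, and nothing says that missing participants count as event-free. What stands is the conflict with the narrower schedule text. How such participants are censored is properly left to the statistical analysis plan.
- A reader might infer that the 6-week visit does not ask about exacerbations. That cannot be known, because the content of the 6-week form is not given. What stands is that no such enquiry is specified.
- A reader might take any extension of the index course as a qualifying event. Lengthening a course is not clearly an increased dose, and is not in itself a worsening. Only a worsening with a step-up clearly meets the wording.
- An inpatient step-up would have to be reported by the participant months later as a repeat exacerbation, which many would not do. This makes misclassification less likely but does not exclude it.
- Onset dates matter only if Cox is used, and section 12b also allows logistic regression. However, a step-up counted as an event distorts a yes/no outcome too.
- Repeat exacerbation is in none of the section 4 objectives or section 5 hypotheses, and the study is exploratory. This limits the weight of the point. It does not make the definition workable.

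**Conclusion.** The point holds for the definition and, more narrowly, for timing and fallback. As written, escalation of index treatment meets the definition of a repeat exacerbation and can enter the analysis near time zero. No collection is specified before 3 months, so early dates for community-treated events would rest on recall of up to about 13 weeks. The passages on participants who cannot be reached disagree about what may be collected.

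The size cannot be stated from the protocol. It gives no rate for index escalation, for community-treated exacerbations or for failed contact, so the number of affected participants and the effect on the hazard ratio are unknown. The 12, 16 and 28 of 80 above rest on upper-end background readmission rates and, for day 42, on a constant hazard. They only illustrate early activity. The primary outcome, based on discharge diagnosis, is not affected. The change should be made because it is nearly free, but the point concerns one secondary outcome of an exploratory cohort.

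**What to change.** 1. At the existing 6-week visit, ask whether there has been an exacerbation since discharge and record its onset date. Recall at the later calls stays at three months, so this improves only the first interval.
2. In section 10b, use the same treatment wording as section 8. Count an event only if it begins after index discharge and after the index treatment course has ended. Report earlier escalation separately, as non-response of the index episode.
3. Reconcile the follow-up schedule in section 11c with the main text of that section and with section 13. State that next-of-kin or practice reports may supply this outcome when the participant cannot be reached, and amend the self-report wording in section 10b to match.

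The cost is one extra question, a few wording changes and slightly fewer counted events. No visit is added and treatment is not touched. Asking the practice for treatment dates in every participant would go further, but it is a matter of preference and this point does not require it.

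### Repeat exacerbation (10b) uses a different treatment wording from Section 8 and rests on self-report alone, so a documented COPD readmission need not count as an exacerbation

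*Protocol*

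**What the plan says.** Three parts of the protocol bear on what counts as an exacerbation.

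- **Section 8 (index event):** "An AECOPD is defined as acute worsening of respiratory symptoms that results in additional therapy: antibiotics and/or systemic corticosteroids".
- **Section 10a (primary outcome):** "Hospital re-admission for COPD within 12 months defined as admitted to hospital, excluding emergency department presentation only". The source is a document: the admission counts "with discharge diagnosis on the discharge summary being" an exacerbation of COPD. There is no treatment criterion.
- **Section 10b (repeat exacerbation):** a worsening of symptoms that "results in increased dose of systemic corticosteroids and /or antibiotics. This outcome will be self reported".

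On data collection, Section 11c states: "A further questionnaire via phone contact will be performed at 3, 6, 9 & 12 months". If the patient cannot be reached, Sections 11c and 13 allow contact with the nominated next of kin and the general practitioner. In the Section 11c list of follow-up contacts, the purpose given for the discharge summaries obtained this way is to settle the primary outcome. Section 12b then models time to readmission and time to repeat exacerbation as two secondary outcomes, by Cox or logistic regression.

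**The concern.** An admission for a COPD exacerbation is the severe form of a COPD exacerbation. One therefore expects the repeat-exacerbation outcome to contain every COPD readmission, and the time to first exacerbation never to exceed the time to first readmission. The protocol does not secure this. The treatment criterion in 10b is worded more narrowly than in Section 8, and the source for 10b is the patient's own account while the source for 10a is the discharge summary.

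At stake is the coherence of the secondary analyses. If the two outcomes are not nested, one patient can carry a primary event and no exacerbation, and the FeNO associations with the two outcomes describe events ascertained in different ways. The wording in 10b will presumably also shape the phone questionnaire, so an event treated outside hospital that is missed for this reason may not be recoverable at analysis.

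**Working it through.** The protocol states no figure on this point, so there is nothing to reproduce. The check compares the definitions and follows individual patients through them.

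**Definitions side by side**

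| | Section 8 | Section 10a | Section 10b |
|---|---|---|---|
| Symptoms | acute worsening | none stated | acute worsening |
| Treatment | additional therapy | none stated | increased dose |
| Drugs | antibiotics and/or systemic corticosteroids | not applicable | same two classes |
| Source | hospital admission | discharge summary | self-report |

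**Following patients through the rules.** Let R be the time of a COPD readmission meeting 10a, and E the time of the first repeat exacerbation under 10b. Nesting requires E ≤ R for every readmitted patient.

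1. The patient is readmitted, reports it and describes the treatment as an increase. Both outcomes are positive and E ≤ R. No conflict.
2. The patient is readmitted and a summary is on file, but the patient does not report the episode. 10a is positive and 10b is negative. E is censored although R is observed.
3. As in 2, but the patient later reports a course treated in the community. Both outcomes are positive, but E > R: the first exacerbation is dated after the readmission.
4. The patient cannot be reached, and the next of kin or general practitioner supplies the information. 10a is positive. 10b is unsettled, because such a report is not self-report.
5. The patient reports the admission, but the treatment is not taken to be an increased dose. 10a is positive and 10b is negative on the literal wording.

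No sentence in the protocol resolves cases 2 to 5. With calls at 3, 6, 9 and 12 months, recall covers about three months each time, so a self-reported date is also weaker than the admission date on a discharge summary.

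**Size, as illustration only.** The one readmission figure near this point is in Section 2 (Background): up to 35% readmitted at 90 days. It is an upper figure and is not stated to be COPD-specific. If it applied to all 80 patients, 0.35 × 80 = 28 would be readmitted by then. The protocol gives no non-reporting rate. Over an assumed range of 5% to 30%, 0.05 × 28 = 1.4 and 0.30 × 28 = 8.4. So even with the ceiling figure and every readmission treated as COPD, about 1 to 8 patients would be discordant. This is a ceiling calculation under assumptions, not an estimate.

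**The case against.** The strongest case against has four parts.

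*The wording difference is loose drafting.* Both definitions start from acute worsening and name the same drugs, and a new course can be read as an increase from zero. This largely stands. The wording should be aligned, but the missing link between self-report and records is the stronger part and does not depend on it.

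*There are safeguards.* Sections 11c and 13 provide next-of-kin and general-practitioner contact when calls fail, and Section 13 obtains consent for this in respect of the follow-up calls themselves. A patient in hospital at one call can report at the next. This reduces the loss, but it does not say that a proxy report or a retrieved summary counts towards 10b, which is stated to be self-reported.

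*Self-report is a reasonable choice.* Events treated in the community produce no discharge summary. This stands for those events, and the fix keeps it. It gives no reason to ignore a summary where one exists.

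*A derivation rule may sit in the SAP.* That would be a good answer if the protocol were silent. It is not: it fixes the source of this outcome, and a SAP rule counting readmissions would depart from that text.

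A reader might also infer more than the protocol supports:

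- That 28 patients will have certain exacerbations at risk of omission. The 35% is an upper figure for readmission not stated to be COPD-specific, so it does not count 10a events.
- That an exacerbation count is biased downward. There is no count outcome. Missed events would lengthen time to exacerbation, but self-report can also add events, so the net direction is not shown.
- That the exacerbation and readmission associations cannot be compared at all. A few discordant patients would not make this so, and nothing in the protocol ties non-reporting to FeNO.

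**Conclusion.** The point holds as a defect in a stated outcome definition. Sections 8 and 10b word the same event differently, and 10b relies on self-report even where the study holds a discharge summary. A confirmed COPD readmission can therefore be scored as no exacerbation, or the first exacerbation can be dated after it, and the two time-to-event outcomes in Section 12b need not be nested.

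Severity is minor to moderate. The number of patients affected is unknown and probably small, since most readmitted patients are likely to receive one of the named treatments and to recall the admission; that is a judgement, not a figure from the protocol. The primary outcome and time to readmission are untouched. Repeat exacerbation is one secondary outcome in an exploratory study and appears in none of the six objectives in Section 4. The conclusion assumes only that 10b is applied as written.

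**What to change.** Make two changes in Section 10b and match the phone form to them.

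1. Define repeat exacerbation in the Section 8 words: "acute worsening of respiratory symptoms that results in additional therapy: antibiotics and/or systemic corticosteroids". Do not add a clause for a change of agent. Section 8 has none, and it could score a switch within one ongoing episode as a new event.
2. State that every readmission meeting 10a counts as a repeat exacerbation on its admission date, whether or not the patient reports it. Keep self-report for events treated outside hospital, and accept a next-of-kin or general-practitioner report when the patient cannot be reached.

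The cost is a few sentences and no new data collection, because the discharge summary is already needed for the primary outcome. The change concerns outcome definition only and touches no treatment. The small downside is that hospital and community events come from different sources; this should be noted when the results are reported.
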